5.1.2 Definition of DLT

Dose-limiting toxicities (DLTs) will be evaluated during the run-in phase consisting of the first 6 patients enrolled in this trial. The period for evaluating DLTs will be from the time of first administration of nivolumab and ipilimumab until 12 weeks. Adverse event monitoring will continue for these subjects throughout the course of their treatment as outlined in the Schedule of Study Assessments, these adverse events will include potential XRT related toxicities. Subjects who do not remain on the study up to this time for reasons other than DLT will be replaced with another subject. Grading of DLTs will follow the guidelines provided in the Common Terminology Criteria for Adverse Events (CTCAE) version 5.0.

A DLT will be defined as any Grade 3 or higher toxicity that occurs during the DLT evaluation period. Toxicity that is clearly and directly related to the primary disease or to another etiology is excluded from this definition. The following will be DLTs:

- Any Grade 4 irAE
- Any \geq Grade 3 colitis
- Any Grade 3 or 4 noninfectious pneumonitis irrespective of duration

- Any Grade 2 pneumonitis that does not resolve to \leq Grade 1 within 3 days of the initiation of maximal supportive care
- Any Grade 3 irAE, excluding colitis or pneumonitis, that does not downgrade to Grade 2 within 3 days after onset of the event despite optimal medical management including systemic corticosteroids or does not downgrade to \leq Grade 1 or baseline within 14 days
- Liver transaminase elevation $> 8 \times$ ULN or total bilirubin $> 5 \times$ ULN
- Any \geq Grade 3 non-irAE, except for the exclusions listed below
 - Grade 3 fatigue lasting \leq 7 days
 - Grade 3 endocrine disorder (thyroid, pituitary, and/or adrenal insufficiency) that is managed with or without systemic corticosteroid therapy and/or hormone replacement therapy and the subject is asymptomatic
 - Grade 3 inflammatory reaction attributed to a local antitumor response (e.g., inflammatory reaction at sites of metastatic disease, lymph nodes, etc.)
 - Concurrent vitiligo or alopecia of any AE grade
 - Grade 3 infusion-related reaction (first occurrence and in the absence of steroid prophylaxis) that resolves within 6 hours with appropriate clinical management
 - Grade 3 or 4 neutropenia that is not associated with fever or systemic infection that improves by at least 1 grade within 3 days. Grade 3 or Grade 4 febrile neutropenia will be a DLT regardless of duration or reversibility
 - Grade 3 or 4 lymphopenia
 - Grade 3 thrombocytopenia that is not associated with clinically significant bleeding that requires medical intervention, and improves by at least 1 grade within 3 days
 - Isolated Grade 3 electrolyte abnormalities that are not associated with clinical signs or symptoms and are reversed with appropriate maximal medical intervention within 3 days
- Grade 4 hematologic toxicity, not described in exclusions above
- Prolonged delay (>2 weeks) in initiating second dose of nivolumab or ipilimumab due to treatment-related toxicity
- Grade 5 toxicity, i.e., death

Dose modification/delays according to Section 5.1.3 will apply to the patients who experience DLTs in the run-in phase.

Immune-related AEs are defined as AEs of an immune nature (i.e., inflammatory) in the absence of a clear alternative etiology. In the absence of a clinically significant abnormality, repeat laboratory testing will be conducted to confirm significant laboratory findings prior to designation as a DLT.

During this DLT period, patients who received <90% of the nivolumab OR ipilimumab infusion on day 1 (e.g., because the infusion of either drug had to be discontinued due to an infusion reaction) and did not experience a DLT will not be taken into account in the assessment of the overall DLT rate for the phase I run-in cohort and will be replaced.

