Study Design

This is a single arm, open label, prospective study evaluating the safety and clinical efficacy of the combination of nivolumab, ipilimumab and hypofractionated palliative radiation therapy (SBRT) in patients with advanced salivary gland cancer.

Patients enrolled will receive the following treatment (see Section 5.1.1):

1. Nivolumab 3mg/kg IV Q 2 weeks x 12 doses followed by Nivolumab 480 mg IV Q4 weeks x 8 doses
2. Ipilimumab 1 mg/kg IV Q6 weeks x 4 doses
3. Hypofractionated radiation therapy (SBRT) given to a total dose of 24Gy given in 3 fractions every other day over 1 week and initiated 2 weeks after the first dose of nivolumab and ipilimumab. The target lesion will be a local/regional or metastatic disease site that per the multidisciplinary head and neck team, requires local control for palliation and/or prevention of impending symptoms.

Both nivolumab and ipilimumab have well established toxicity profiles as a single agent and in combination. However, since the combination of nivolumab, ipilimumab and palliative radiation has not previously been described or studied, the first 6 patients who will be enrolled in this study will represent the initial safety run-in phase. Patients will receive full dose nivolumab and ipilimumab. Enrollment will be halted until these first 6 patients complete the first 12 weeks of treatment and acute toxicities will be reviewed. If more than 2 DLTs (to be defined in Section 5.1.2) are noted in this 6 patient cohort, a dose modification will be implemented (Section 5.1.1) for the remaining 14 patients who will be enrolled in the expansion cohort. Enrollment period is 24 months and duration of the trial 48 months.

Study Population

The study aims to enroll patients with salivary gland carcinomas (WHO, 2005), who are not candidates for curative intent therapy and who have a target lesion (either local/regional or distant metastatic site involving the lung and/or bone), that requires local control for palliation, as determined by a multidisciplinary team.

Inclusion Criteria:

1. Histologically proven salivary gland carcinoma (WHO, 2005) arising from a previous head and neck primary site, and located within the head and neck region, lung or bone, and who are not candidates for curative intent therapy.
2. ≥ 18 years old at the time of signing informed consent.

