4.2 Study Schema

Note: refer to Dosing and Administration (Section 5.1.1) for further details on treatment scenarios.

Clinical Study Protocol RG1718030
Drug Substance: Nivolumab and Ipilimumab
IND Number:140818
Protocol version 3.0 April 17, 2019

Both ipilimumab and nivolumab are FDA approved, and the safety profile of both agents have been extensively studied. However, because the combination with radiation has not been previously studied, the first 6 patients of this study will represent the initial run-in phase of the triplet combination of nivolumab, ipilimumab and palliative radiation. The initial doses of ipilimumab and nivolumab will be administered on day 1 of therapy.

Stereotactic radiation will be initiated on Week 3 of treatment. SBRT will be delivered to a total dose of 24 Gy, given in 3 fractions of 8Gy every other day. Treatment will be continued according to the study schema unless patient withdraws consent, has confirmed disease progression, and/or develops toxicity that results in treatment discontinuation.

Enrollment will be halted until these first 6 patients complete the first 12 weeks of treatment and acute toxicities will be reviewed. If more than 2 DLTs (to be defined in Section 5.1.2) are noted in this six patient cohort, a dose modification will be implemented (Section 5.1.1) for the remaining 14 patients who will be enrolled in the expansion cohort.

Serum correlative studies will be collected at the following timepoints: at baseline, prior to week 8, and prior to week 16 of treatment. Archived formalin fixed paraffin embedded tissue (obtained in the 12 months prior to trial enrollment) will be collected from patients enrolled. If the patient does not have archived tissue available, a fresh biopsy will be obtained. Tissue requirement will be waived if deemed contraindicated or not clinically available/accessible for resection per the treating physician (PI approval required).

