5. TREATMENT

5.1 Systemic Therapy

5.1.1 Dosage and Administration

The treatment to be used in the run-in phase (initial 6 patients) of this trial is outlined in the table below. If ≤ 1 DLT is observed in the run-in phase, then the remaining 14 patients will be provided treatment per the following:

Drugs	Dose/Potency	Dose Frequency	Route of Administration	Regimen/Treatment Period
Weeks 1-24				
1. Nivolumab	3 mg/kg	Q2 weeks	IV infusion	Maximum of 12 doses
2. Ipilimumab	1mg/kg	Q6 weeks	IV infusion	Maximum of 4 doses
Weeks 25-52				
1. Nivolumab	480mg IV flat dose	Q4 weeks	IV infusion	Maximum of 8 doses

If 2 or more DLTs (defined in Section 5.1.2) are observed in the run-in phase, the following treatment will be used for the remaining 14 patients to be treated on the clinical trial protocol:

Drugs	Dose/Potency	Dose Frequency	Route of Administration	Regimen/Treatment Period
Weeks 1-24				
1. Nivolumab	3 mg/kg	Q4 weeks	IV infusion	Maximum of 6 doses
2. Ipilimumab	1mg/kg	Q8 weeks	IV infusion	Maximum of 3 doses
Weeks 25-52				
1. Nivolumab	480mg IV flat dose	Q6 weeks	IV infusion	Maximum of 4 doses

Patients who experience a DLT in the run-in phase, will have dose interruptions/reductions as outlined in Section 5.1.3.

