5.1.3.1 Dose Delay Criteria

Doses of both nivolumab and ipilimumab (during study weeks 1-24) or nivolumab alone (during study weeks 25-52) should be held if any of the following are observed:

- Any Grade ≥ 3 non-skin, drug-related adverse event, except for fatigue and laboratory abnormalities

- Any Grade ≥ 3 drug-related laboratory abnormality with the following exceptions for lymphopenia, aspartate aminotransferase (AST), alanine aminotransferase (ALT), or total bilirubin or asymptomatic amylase or lipase:
 - Grade 3 lymphopenia does not require a dose delay
 - If a subject has a baseline AST, ALT, or total bilirubin that is within normal limits, delay dosing for drug-related Grade 2 toxicity
 - If a subject has baseline AST, ALT, or total bilirubin within the Grade 1 toxicity range, delay dosing for drug-related Grade ≥ 3 toxicity
 - Any Grade ≥ 3 drug-related amylase or lipase abnormality that is not associated with symptoms or clinical manifestations of pancreatitis does not require dose delay.
- Any AE, laboratory abnormality or inter-current illness which, in the judgment of the investigator, warrants delaying the dose of study medication.

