8.4 STUDY STOPPING RULE

In keeping with the study primary endpoint, a stopping rule will be implemented in the unlikely event that the combination under study is deemed to have unacceptably high toxicities. Enrollment will be halted if more than 3 patients experience a Grade 4 or higher drug related toxicity (CTCAE v. 5) during the trial treatment period or up to 30 days after the last investigational drug infusion. The likelihood of observing more than 3 Grade 4+ drug-related adverse events is 80% if the true

rate is 20% and the likelihood is 91% if the true rate is 25%. This rule has an 83% chance of prematurely discontinuing trial enrollment after the 1st 10 patients are enrolled if the true rate of Grade 4 drug related toxicity is 40%. The study will be reviewed by the University of Washington/Fred Hutch Cancer Consortium Data and Safety Monitoring Committee (DSMC

STATISTICAL CONSIDERATIONS

All patients enrolled in the study, including those in the run-in phase will be included in the analysis of toxicity and efficacy.

Safety and tolerability is the primary endpoint of this study, and all patients enrolled will be assessed for this endpoint. Adverse events will be recorded and graded based on CTCAE v. 5, and their relationship to the experimental agents reported.

Similarly, all patients enrolled in the study (i.e., the initial 6 patient cohort, and the additional 14 patient expansion) will be included in the efficacy analyses. Clinical responses to the combination of nivolumab, ipilimumab and hypofractionated radiation will be based on RECIST 1.1 criteria. Oncologic outcome endpoints such as progression free and overall survival will be calculated from the date of study enrollment, until disease progression or death from any cause, respectively. Survival estimates will be calculated using the Kaplan-Meier method.

Exploratory endpoints of this study include correlative work performed on research serum and tissue samples.

Sample size determination

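### The run-in rule contradicts itself: at exactly 2 DLTs in the first 6 patients, Section 5.1.1 reduces dosing for the remaining 14, while the synopsis and Section 4.2 do not

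*Combined protocol and SAP*

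**What the plan says.** The first 6 patients form a safety run-in on the full schedule. Section 5.1.2 ties the DLT count to them: "Dose-limiting toxicities (DLTs) will be evaluated during the run-in phase consisting of the first 6 patients enrolled in this trial". Enrolment stops until they have completed 12 weeks, and the DLTs seen in them decide what the remaining 14 receive.

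The trigger appears in three places in the current text:

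- Synopsis, Study Design: "If more than 2 DLTs (to be defined in Section 5.1.2) are noted in this 6 patient cohort", the modification described in Section 5.1.1 is applied to the remaining 14.
- Section 4.2, Study Schema: "If more than 2 DLTs (to be defined in Section 5.1.2) are noted in this six patient cohort", with the same consequence and the same cross-reference.
- Section 5.1.1: the full schedule continues at 1 DLT or fewer. "If 2 or more DLTs (defined in Section 5.1.2) are observed in the run-in phase", then "the following treatment will be used for the remaining 14 patients to be treated on the clinical trial protocol", namely the reduced-frequency table.

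The two schedules in Section 5.1.1 differ materially. The nivolumab maximum falls from 12 + 8 = 20 doses to 6 + 4 = 10, and the ipilimumab maximum from 4 to 3.

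On the unit of counting, all three triggers refer to DLTs rather than to patients. Other wording points to patients. Section 5.1.2 says that patients who received too little of the day-1 infusion and had no DLT "will not be taken into account in the assessment of the overall DLT rate for the phase I run-in cohort and will be replaced". The closing sentence of Section 5.1.1 also refers to individual patients who have a DLT.

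**The concern.** The run-in is the only point at which the protocol sets the dosing schedule from accumulating data, and safety is the primary objective. At a count of exactly 2, Section 5.1.1 orders the reduced schedule. The trigger in the synopsis and Section 4.2 is not met, which implies the full schedule. I find nothing in the document that says which section takes precedence.

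If that count occurs, someone must choose the schedule for 14 of 20 patients after seeing the toxicity data. The operating characteristics of the run-in cannot be stated until the rule is settled. The toxicity analysis pools all 20 patients, so the choice also determines whether the primary estimate describes one schedule or a 6-and-14 mixture of two.

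A smaller ambiguity sits beside this. Read literally, one patient with two qualifying events would meet the Section 5.1.1 trigger alone.

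**Working it through.** The plan gives no operating characteristic for the run-in, so there is no figure of its own to reproduce.

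**Inputs**

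- Run-in size n = 6 (synopsis; Sections 4.2 and 5.1.2).
- Trigger A: 2 or more (Section 5.1.1). Trigger B: more than 2, that is 3 or more (synopsis; Section 4.2).
- True probability p that a patient has a DLT within 12 weeks: not given, so taken over 10–50%. The sample-size text uses 30% for Grade 3 or higher acute drug-related toxicity. That is a different quantity from a DLT, so 30% serves here only as an illustration within the range.

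**Action by count**

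| DLTs in the run-in | Section 5.1.1 | Synopsis and Section 4.2 |
|---|---|---|
| 0 or 1 | full schedule | trigger not met |
| 2 | reduced frequency | trigger not met |
| 3 or more | reduced frequency | reduced frequency |

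Only the middle row conflicts.

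**Formula**

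Counting each patient at most once, X ~ Binomial(6, p), so P(X = k) = C(6,k) p^k (1 − p)^(6−k).

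At p = 0.30:

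- P(X = 0) = 0.7^6 = 0.118
- P(X = 1) = 6 × 0.3 × 0.7^5 = 0.303
- P(X = 2) = 15 × 0.3² × 0.7^4 = 0.324
- Trigger A: 1 − 0.118 − 0.303 = 0.580 (unrounded inputs)
- Trigger B: 0.580 − 0.324 = 0.256

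**Results over the range**

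| Assumed p | Exactly 2 (texts conflict) | Reduce, trigger A | Reduce, trigger B |
|---|---|---|---|
| 10% | 9.8% | 11.4% | 1.6% |
| 20% | 24.6% | 34.5% | 9.9% |
| 30% | 32.4% | 58.0% | 25.6% |
| 40% | 31.1% | 76.7% | 45.6% |
| 50% | 23.4% | 89.1% | 65.6% |

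The gap between the last two columns equals the first probability column, as it must. At 30%, 2 is the most likely single count, since P(X = 3) = 20 × 0.3³ × 0.7³ = 0.185 is below 0.324.

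**Unit of counting**

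The number of events is never smaller than the number of patients with an event. Counting events would therefore make either trigger at least as likely as shown. The documents do not allow the increase to be sized.

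**The case against.** The best reply is that a careful reader can resolve the conflict. The synopsis is a summary, both other texts refer to Section 5.1.1 for the modification, and Section 5.1.1 gives a complete rule with a continue side and a modify side. That supports Section 5.1.1 as the default. It does not remove the contradiction: Section 4.2 is body text, and the looser trigger appears twice. On the unit, the phrase about an overall DLT rate and the reference to patients who have a DLT support a per-patient count. That matter needs clarification and is not a separate defect.

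A reader might go further. Because DLTs are evaluated only in the first 6, one could infer that the reduced schedule goes to 14 patients without safety control, so that a second DLT cohort is required. The premise is correct, but the inference is not supported:

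- The reduced schedule uses the same drugs, the same dose per administration and the same SBRT, with the drugs given less often. Nothing in the protocol requires a new DLT cohort after such a step. In fairness, the day-1 doses and week-3 SBRT are unchanged, so early risk may not fall.
- Section 8.4 still applies: "Enrollment will be halted if more than 3 patients experience a Grade 4 or higher drug related toxicity". It does not count DLTs below Grade 4. Individual doses "should be held if any of the following are observed" under Section 5.1.3.1, and the resumption and discontinuation criteria of Sections 5.1.3.2 and 5.1.3.3 also remain.
- It would also be too strong to say that only a committee could pause accrual for DLTs below Grade 4. Section 3 gives trial oversight and weekly adverse-event review to the Protocol Director and staff, in addition to the committee review in the Study Management section.
- A second 6-patient check would be weak. At a true 30% it would fail to pause 42% of the time (2 or more) or 74% (more than 2). If the modification halved 30% to 15%, it would still pause 22% or 5% of the time.
- Its reach is short. With even accrual of 20 patients over 24 months, 20/24 × 2.76 months = 2.3 patients enrol during the sixth patient's 12 weeks. That leaves 14 − 6 − 2.3 = 5.7, about 6 patients, still to enrol.

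**Conclusion.** The decision rule is wrong as written. The contradiction is in current protocol text, and it gives opposite schedules for 14 of 20 patients whenever the run-in yields exactly 2 DLTs. The probability of that outcome runs from about 10% to 32% over assumed true rates of 10–50%. At 30%, the two texts differ by 32 percentage points in the chance of reducing dosing (58% against 26%).

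The existence of the conflict rests on no assumption. Its size rests on the assumed DLT rates, on independent patients, and on counting patients rather than events.

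The conclusion stops there. That no DLT count applies to the reduced schedule is a fact about the design, but the documents do not make it an error. Adding such a count is an optional choice with real trade-offs and is not part of the required correction.

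**What to change.** State one trigger, in identical words, in the synopsis, Section 4.2 and Section 5.1.1. Count it as patients with at least one DLT among the 6 evaluable run-in patients, after any replacements under Section 5.1.2.

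Proposed default, for the sponsor to confirm: full schedule if 0 or 1 of 6 has a DLT, reduced schedule if 2 or more do. This leaves the Section 5.1.1 thresholds unchanged and corrects the other two places. If the sponsor intended more than 2, both sides of the rule in Section 5.1.1 must change instead.

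The cost is a short amendment, with no new assessments or patients. The scientific price of the default is a more frequent reduction when the true rate is acceptable: 11% against 2% at a true 10%. The alternative has the opposite price: at a true 40% it would keep the full schedule 54% of the time (1 − 0.456), against 23% (1 − 0.767) under the default.

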5.1.3.3 Criteria for permanent discontinuation of nivolumab and ipilimumab

An individual subject will not receive any further investigational product if any of the following occur in the subject in question:

- The subject or legal representative (such as a parent or legal guardian) withdraws consent.
- Confirmation of PD and investigator determination that the subject is no longer benefiting from treatment with nivolumab and ipilimumab
- Dosing delays lasting 12 weeks or more
- Inability to reduce corticosteroid to a dose of ≤ 10 mg of prednisone per day (or equivalent) **within 12 weeks** after last dose of study drug/study regimen
- Recurrence of a previously experienced Grade 3 treatment-related AE following resumption of dosing
- Adverse event that, in the opinion of the investigator or the sponsor, contraindicates further dosing
- Subject noncompliance that, in the opinion of the investigator or sponsor, warrants withdrawal; e.g., refusal to adhere to scheduled visits
- Subject is determined to have met one or more of the exclusion criteria for study participation at study entry and continuing investigational therapy might constitute a safety risk

- Intercurrent illness that prevents further administration of treatment
- Investigator's decision to withdraw the subject
- The subject has a confirmed positive serum pregnancy test
- Noncompliance with trial treatment or procedure requirements
- The subject is lost to follow-up
- Completed all doses of study drug
- Grade ≥ 3 infusion reaction

Subjects may withdraw consent at any time for any reason or be dropped from the trial at the discretion of the investigator should any untoward effect occur. In addition, a subject may be withdrawn by the investigator or the Sponsor if enrollment into the trial is inappropriate, the trial plan is violated, or for administrative and/or other safety reasons.

Subjects who are permanently discontinued from receiving investigational product will be followed for safety, including the collection of any protocol-specified blood specimens, unless consent is withdrawn or the subject is lost to follow-up or enrolled in another clinical study. All subjects will be followed for survival. Subjects who decline to return to the site for evaluations will be offered follow-up by phone every 3 months as an alternative.

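### Run-in patients who leave before week 12 for toxicity short of a DLT are replaced, so the count that selects the regimen for the other 14 patients leaves them out

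*Combined protocol and SAP*

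**What the plan says.** Section 5.1.2 sets up "the run-in phase consisting of the first 6 patients enrolled in this trial" and fixes the window: "The period for evaluating DLTs will be from the time of first administration of nivolumab and ipilimumab until 12 weeks". On early leavers it says: "Subjects who do not remain on the study up to this time for reasons other than DLT will be replaced with another subject". A further rule in the same section covers patients who received less than 90% of either day-1 infusion. Its own example is a patient whose infusion "had to be discontinued due to an infusion reaction) and did not experience a DLT will not be taken into account"; that patient is also replaced.

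The count decides the regimen for the other 14 patients. Section 5.1.1 keeps the starting schedule "If ≤ 1 DLT is observed in the run-in phase" and changes it "If 2 or more DLTs (defined in Section 5.1.2) are observed in the run-in phase". The Synopsis and Section 4.2 instead require more than 2 DLTs for the change, so the result of exactly 2 is unresolved.

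Section 5.1.3.3 says subjects may "be dropped from the trial at the discretion of the investigator should any untoward effect occur". The paragraph after it keeps patients who permanently stop drug in safety follow-up, unless they withdraw consent, are lost or join another study. One DLT criterion concerns delay: "Prolonged delay (>2 weeks) in initiating second dose of nivolumab or ipilimumab due to treatment-related toxicity".

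**The concern.** The primary objective is safety and tolerability, and the run-in exists because the triplet had not been studied before. A patient who leaves because of the treatment is informative about tolerability. Under 5.1.2 that patient stays in the count only if the reason is a DLT. A patient who leaves for a Grade 2 event, or for a Grade 3 immune-related event before its resolution clock has run, is exchanged for someone else.

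That is exclusion related to outcome, inside the only count with a stated consequence for the regimen. Acute toxicities are also reviewed when enrollment pauses, but no decision is attached to that review except through DLTs. The final toxicity analysis comes after the regimen has been chosen and cannot correct the choice.

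**Working it through.** **Which patients can be lost.** Set side by side, the sections leave three routes.

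1. *Events that meet no listed criterion.* A Grade 2 event other than unresolved pneumonitis is not in the DLT list of 5.1.2, yet 5.1.3.3 allows permanent discontinuation for any adverse event judged to contraindicate dosing.
2. *Events still on a clock.* A Grade 3 immune-related event (other than colitis or pneumonitis) becomes a DLT under the list only after 3 days without downgrading to Grade 2, or 14 days without reaching Grade 1 or baseline. Delay becomes a DLT only after more than 2 weeks, and only for the second dose of either drug. On the starting schedule those doses fall at week 3 (nivolumab) and about week 7 (ipilimumab), so toxicity that first stops later doses is outside this criterion. A patient who leaves while a clock is running has no determined DLT status and becomes replaceable.
3. *Infusion reactions.* A first Grade 3 reaction that resolves within 6 hours, without steroid prophylaxis, is among the exclusions in 5.1.2. Under 5.1.3.3 a Grade 3 or higher infusion reaction ends treatment permanently. If it also cut the day-1 infusion below 90%, the patient is left out of the DLT rate and replaced.

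**Size.** The documents state no operating characteristics for the run-in, so there is no figure to reproduce. They also give no DLT or departure rates, so every input below except n = 6 is an assumption.

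Per-patient 12-week probabilities: DLT pD = 0.20; unrelated departure pO = 0.15; departure for non-DLT toxicity pT = 0.01 to 0.10; completion pC = 1 − pD − pT − pO.

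- Event rate under the rule: pD / (pD + pC)
- Event rate with toxicity leavers counted as events: (pD + pT) / (pD + pT + pC)
- P(2 or more of 6) = 1 − (1 − p)^6 − 6p(1 − p)^5

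For pT = 0.01, pC = 0.64. Rule: 0.20/0.84 = 0.2381, giving 1 − 0.1956 − 0.3668 = 0.4376. Counted: 0.21/0.85 = 0.2471, giving 1 − 0.1822 − 0.3587 = 0.4591.

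For pT = 0.10, pC = 0.55. Rule: 0.20/0.75 = 0.2667, giving 0.5051. Counted: 0.30/0.85 = 0.3529, giving 0.6864.

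| pT | Rate, rule / counted | 2 or more of 6, rule / counted | 3 or more of 6, rule / counted |
|---|---|---|---|
| 1% | 0.238 / 0.247 | 43.8% / 45.9% | 15.1% / 16.5% |
| 2% | 0.241 / 0.259 | 44.4% / 48.7% | 15.5% / 18.4% |
| 5% | 0.250 / 0.294 | 46.6% / 56.7% | 16.9% / 24.5% |
| 10% | 0.267 / 0.353 | 50.5% / 68.6% | 19.7% / 35.9% |

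Both thresholds are shown because the protocol states both.

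**Is the DLT rate itself lowered?** No. Replacement gives pD/(1 − pT − pO), which is never below pD. Here it is 0.238 to 0.267 against 0.20, and a plain 20% gives 34.5% for 2 or more of 6. What the count misses is DLT plus toxicity-related departure. This algebra takes DLT status as known; an event whose clock was cut short is a separate loss that the table does not include.

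**The case against.** The strongest reply is that stopping drug is not leaving the study. Section 5.1.3.3 follows such patients for safety, and adverse events are collected to 100 days after the last dose. On that reading a patient who stops for toxicity stays evaluable, the clocks keep running and few are replaced. This stands in part. However, 5.1.2 does not define remaining on the study, the Synopsis and Section 4.2 pause enrollment until six patients complete 12 weeks of treatment, and 5.1.3.3 also speaks of dropping patients from the trial.

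Second, the DLT definition is broad. It opens with any Grade 3 or higher toxicity, and even the narrower list captures most severe events. This stands and limits the size, but it does not reach Grade 2 events or the listed exclusions.

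Third, the infusion rule concerns exposure: a patient given little drug says little about 12 weeks of it. That is a fair reason to add a patient, but not to leave the reaction out of sight at the decision.

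Fourth, there are other safeguards: weekly review of adverse events, the Grade 4 stopping rule in 8.4 and DSMC review. They stand, but none of them restores these patients to the run-in count.

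A reader might also infer that the replacement rule contradicts the delay criterion. It does not. The two can operate together; the gap is that a departure can come before the 2 weeks are up.

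**Conclusion.** The point holds for the run-in decision only. The count that selects the regimen for 14 patients omits toxicity-related departures that are not DLTs, and can lose DLTs whose status was still open.

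Two stronger readings are tempting and are not supported. One is that the rule understates the DLT rate; the algebra shows that it does not. The other is that it biases the primary safety result; Statistical Considerations includes all enrolled patients, run-in patients among them, in the toxicity analysis.

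The size cannot be fixed from the documents. With 20% DLT and 15% unrelated departure assumed, the gap in the chance of 2 or more of 6 is about 2 points at 1% toxicity departure (45.9 − 43.8), about 4 at 2% (48.7 − 44.4) and about 18 at 10% (68.6 − 50.5). The comparator is a composite that the protocol does not claim to count. The figures therefore show what the count leaves out; they do not show an error in a stated quantity.

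**What to change.** 1. In 5.1.2, allow replacement only for departures unrelated to treatment toxicity, and limit the under-90% infusion exclusion in the same way.
2. In 5.1.3.3, change the wording on dropping subjects from the trial to discontinuing study treatment, so that these patients stay in safety follow-up to week 12 and their DLT status is determined. Where consent is withdrawn first, list the status as undetermined.
3. At the run-in decision, report the DLT count alone and again with toxicity-related departures added.
4. Do not make such departures a new DLT or dose trigger. The sponsor should state, before the run-in is read, how they bear on the regimen decision.
5. Reconcile remaining on the study (5.1.2) with completing 12 weeks of treatment (Synopsis, 4.2) and with follow-up after stopping drug (5.1.3.3). Reconcile the Grade 3 infusion reaction that is not a DLT (5.1.2) with the Grade 3 or higher reaction that ends treatment (5.1.3.3). Also reconcile the two run-in thresholds.

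The cost is slightly more follow-up and reporting, and possibly a less favorable run-in picture. Step 4 matters because of one side effect. If retained toxicity leavers all prove not to be DLTs, the DLT-only rate is 0.20/0.85 = 0.235 and the chance of 2 or more of 6 is 1 − 0.2000 − 0.3692 = 43.1%, below the 50.5% under the present rule at 10% toxicity departure. The DLT-only count should therefore not be read without the second one.
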